**Diagnosis and Main Eligibility Criteria:**

Medically stable HIV-1 infected women who meet the following criteria:

- Currently on a stable antiretroviral regimen consisting of E/C/F/TAF, E/C/F/TDF, or ATV+RTV+FTC/TDF continuously for  $\geq 12$  consecutive weeks preceding the screening visit
- Documented plasma HIV-1 RNA levels  $< 50$  copies/mL for  $\geq 12$  weeks preceding the Screening visit. After reaching HIV-1 RNA  $< 50$  copies/mL, single values of HIV-1 RNA  $\geq 50$  copies/mL followed by re-suppression to  $< 50$  copies/mL is allowed
- HIV-1 RNA  $< 50$  copies/mL at screening
- Estimated glomerular filtration rate (eGFR)  $\geq 50$  mL/min according to the Cockcroft-Gault (C-G) formula at the screening visit

**Study Procedures/  
Frequency:**

After screening procedures, eligible subjects will be randomized 1:1 to Treatment Group 1 or Treatment Group 2 and treated for 48 weeks. Following the Screening and Day 1 visits, subjects will return for study visits at Weeks 4, 8, 12, and then every 12 weeks until the Week 48 visit.

For all eligible subjects, blood and urine will be collected at Day 1, Weeks 4, 8, 12, and then every 12 weeks through the Week 48 visit. Laboratory analyses (including hematology, chemistry, and urinalysis), HIV-1 RNA, CD4+ cell count, and complete or symptom directed physical examinations will be performed at the Screening, Day 1, and all subsequent study visits.

Adverse events and concomitant medications will be assessed at each visit.

---

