**Statistical Methods:**

The primary analysis will consist of a non-inferiority test of switching to GS-9883/F/TAF FDC versus SBR with respect to the proportion of subjects with HIV-1 RNA  $\geq 50$  copies/mL at Week 48 as determined by the US FDA-defined snapshot algorithm. It will be concluded that GS-9883/F/TAF is non-inferior to SBR if the upper bound of the 2-sided 95% confidence interval (CI) of the difference between treatment groups (GS-9883/F/TAF – SBR) in the proportion of subjects with HIV-1 RNA  $\geq 50$  copies/mL is less than 4%; ie, a margin of 4% is applied to non-inferiority assessment. The 2-sided 95% CIs will be constructed based on the exact method.

The proportion of subjects with HIV-1 RNA  $< 50$  copies/mL at Week 48 as determined by the US FDA-defined snapshot algorithm will also be summarized. The 95% CIs will be constructed in the same manner as described for the primary efficacy endpoint.

The change from baseline in CD4+ cell count at Week 48 will be summarized by treatment using descriptive statistics. The differences and the associated 95% CIs will be constructed using Analysis of Variance (ANOVA) model, including treatment (GS-9883/F/TAF vs. SBR) as a fixed effect in the model.

Adverse events and clinical laboratory assessments will be summarized using descriptive statistics.

A total of approximately 470 HIV-1 infected women, randomized in a 1:1 ratio to 2 treatment groups (approximately 235 subjects per treatment group), achieves at least 87% power to detect a non-inferiority margin of 4% difference in the percentage of subjects with HIV-1 RNA  $\geq$  50 copies/mL at Week 48 between the 2 treatment groups.

For sample size and power computation, it is assumed that both treatment groups have 2% of subjects with HIV-1 RNA  $\geq$  50 copies/mL at Week 48 (based on the historical Gilead Genvoya® (GEN) and Stribild® (STB) studies), that a non-inferiority margin is 4%, and that the significance level of the test is at a one-sided 0.025 level.

---

This study will be conducted in accordance with the guidelines of Good Clinical Practice (GCP) including archiving of essential documents.

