### 1.2.3.5. Efficacy Results

Virologic success at Week 12 and 24 was assessed using the US FDA-defined snapshot algorithm, defined as plasma HIV-1 RNA < 50 copies/mL. At Weeks 12 and 24, virologic success was high and similar between the 2 treatment groups as follows: Week 12 GS-9883+F/TAF 93.8%; DTG+F/TAF 93.9% (stratum-adjusted difference in percentages: -1.3%; 95% CI: -12.9% to 10.2%; p = 0.79); Week 24 GS-9883+F/TAF 95.4%, DTG+F/TAF 93.9% (1.0%; 95%CI: -10.7% to 12.7%; p = 0.84).

Of the 5 subjects with baseline viral load > 400,000 copies/mL, 4 had HIV-1 RNA < 50 copies/mL at Week 24, and 1 was considered a virologic failure by US FDA-defined snapshot algorithm with HIV-1 RNA of 60 copies/mL.

Following initiation of study drug, the increases from baseline in CD4 cell count were similar between treatment groups. Mean (SD) baseline CD4 cell counts were as follows: GS-9883+F/TAF 471 (190.9) cells/ $\mu$ L; DTG+F/TAF 507 (271.0) cells/ $\mu$ L; p = 0.35. The mean (SD) change in CD4 cell count from baseline to Week 12 was similar between the 2 treatment groups as follows: GS-9883+F/TAF +170 (150.0) cells/ $\mu$ L; DTG+F/TAF +173 (220.5) cells/ $\mu$ L (difference in LSM: 0; 95% CI: -76 to 76; p = 1.00). There were similar increases in the mean (SD) CD4 cell count in both treatment groups at Week 24: GS-9883/F/TAF, +189 (177.8) cells/ $\mu$ L; DTG+F/TAF, +157 (163.2) cells/ $\mu$ L (difference in LSM: 39; 95% CI: -35 to 113; p = 0.30)

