## 5. INVESTIGATIONAL MEDICINAL PRODUCTS

### 5.1. Randomization

Subjects will be assigned a screening number at the time of consent. **Randomization and Day 1 visit cannot occur until subject eligibility has been confirmed.**

Once eligibility has been confirmed and prior to or during the Day 1 visit the Investigator or designee will randomize the subject using the Interactive Web Response System (IWRS). Once a subject number has been assigned to a subject, it will not be reassigned to any other subject. The subject number assignment and randomization may be performed up to 3 days prior to the in-clinic Day 1 visit provided that all screening procedures have been completed and subject eligibility has been confirmed.

Subjects will be randomized in a 1:1 ratio to Treatment Group 1 or Treatment Group 2.

- **Treatment Group 1:** FDC of GS-9883 50 mg/emtricitabine 200 mg/tenofovir alafenamide 25 mg (GS-9883/F/TAF) administered orally, once daily, without regard to food (approximately n = 235)
- **Treatment Group 2:** Stay on baseline regimen (SBR), including E/C/F/TAF, E/C/F/TDF or ATV+RTV+FTC/TDF administered orally, once daily, with food (approximately n = 235)

The IWRS will assign study drug bottle numbers of open label FDC of GS-9883/F/TAF, open label E/C/F/TAF, open label E/C/F/TDF or open label ATV+RTV+FTC/TDF at each study visit for each subject.

Randomization will be stratified by the prior treatment regimen group (ie, E/C/F/TAF, E/C/F/TDF and ATV+RTV+FTC/TDF).

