#### 8.5.2. Secondary Analyses

The proportion of subjects with HIV-1 RNA < 50 copies/mL at Week 48 as determined by the US FDA-defined snapshot algorithm will also be evaluated. The 95% CIs will be constructed in the same manner as for the primary efficacy endpoint. However, non-inferiority will be assessed using a margin of 10%. It will be concluded that GS-9883/F/TAF is non-inferior to SBR if the lower bound of the 2-sided 95% CI of the difference between treatment groups (GS-9883/F/TAF - SBR) in the response rate is greater than -10%.

The changes from baseline in CD4+ cell count at Week 48 will be summarized by treatment using descriptive statistics. The differences in changes from baseline in CD4+ cell count between the 2 treatment groups and the associated 95% CIs will be constructed using ANOVA models, including treatment (GS-9883/F/TAF vs. SBR) as a fixed effect in the model.

In addition, missing CD4+ cell count will be imputed using Last Observation Carried Forward (LOCF) method and analyzed similarly.

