2.2. Week 48 Interim Analysis

The Week 48 interim analysis was conducted after all subjects either completed their Week 48 visit or prematurely discontinued from the study drug.

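### The Week 48 CD4+ comparison lists treatment as its only model term; it is valid, but adding baseline CD4+ and the randomisation stratum could narrow its confidence interval at no data cost

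*Protocol*

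**What the plan says.** Change from baseline in CD4+ count at Week 48 is a named secondary endpoint (protocol 3.1 and 8.1.3). Protocol 8.5.2 states that the group differences and their 95% CIs "will be constructed using ANOVA models, including treatment (GS-9883/F/TAF vs. SBR) as a fixed effect in the model". The synopsis, under Statistical Methods, gives the same ANOVA, "including treatment (GS-9883/F/TAF vs. SBR) as a fixed effect in the model". Protocol 8.5.2 adds a second version in which "missing CD4+ cell count will be imputed using Last Observation Carried Forward (LOCF) method and analyzed similarly", so it inherits the same model.

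Both candidate covariates are available. The synopsis states that "CD4+ cell count, and complete or symptom directed physical examinations will be performed at the Screening, Day 1, and all subsequent study visits", and protocol 6.2.2 lists CD4+ among the Day 1 blood tests. Protocol 5.1 states: "Randomization will be stratified by the prior treatment regimen group (ie, E/C/F/TAF, E/C/F/TDF and ATV+RTV+FTC/TDF", which gives three strata.

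The supplied SAP covers only the final analysis of subjects exposed to B/F/TAF (SAP 2.3 and 3). On the randomised comparison it reports: "The Week 48 interim analysis was conducted after all subjects either completed their Week 48 visit or prematurely discontinued from the study drug". The SAP that governed that analysis is not among the documents.

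**The concern.** A change score subtracts baseline with a coefficient fixed at 1. The most efficient coefficient is the regression slope of the Week 48 value on the baseline value. Where that slope differs from 1, the change score carries avoidable variance that a baseline term would remove.

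The stratum raises a separate matter. Stratified randomisation balances prior regimen between the arms. A model that ignores the stratum still counts any between-stratum variation as noise, so its standard error is somewhat too large if prior regimen predicts CD4+ change.

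What is at stake is the width of one secondary confidence interval. No margin, decision rule or sample size depends on CD4+.

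**Working it through.** **The plan's own figure.** No power or precision is stated for CD4+. The one stated power concerns the primary endpoint (protocol 8.8: 235 per arm, 2% in both arms, margin 4%, one-sided 0.025). It reproduces: Φ(0.04/√(2×0.02×0.98/235) − 1.96) = Φ(1.137) = 87.2%, against at least 87% stated. It does not involve CD4+.

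**Baseline term.** Let s0 be the baseline SD, k the ratio of Week 48 SD to baseline SD, r the correlation and b = rk the slope.

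- Variance of change: s0²(1 + k² − 2rk)
- Variance after baseline adjustment: s0²k²(1 − r²)
- Difference: s0²(1 − b)², never negative and zero only at b = 1
- CI-width ratio, adjusted to unadjusted: √[k²(1 − r²)/(1 + k² − 2rk)]

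Example at k = 1, r = 0.7: √(0.51/0.60) = 0.922, so the interval is 7.8% narrower. The documents give no r or k for suppressed women, so a range is shown:

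| k | r = 0.5 | r = 0.7 | r = 0.9 |
|---|---|---|---|
| 0.9 | 18.3% | 13.3% | 10.0% |
| 1.0 | 13.4% | 7.8% | 2.5% |
| 1.1 | 9.6% | 4.0% | 0.0% |
| 1.2 | 6.7% | 1.7% | 1.1% |

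At b = 1 (for example k = 1.2, r = 0.833) there is no gain. The simulated width ratio there was 1.001, a cost of about 0.1%.

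**Scale in cells/µL, illustration only.** Protocol 1.2.3.5 gives Phase 2 SDs for treatment-naive subjects: baseline 190.9 and 271.0, Week 24 change 177.8 and 163.2, with arms of 65 and 33 (protocol 1.2.3.4).

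- Pooled baseline SD: √[(64×190.9² + 32×271.0²)/96] = 220.9
- Pooled change SD: √[(64×177.8² + 32×163.2²)/96] = 173.1
- Unadjusted half-width at 235 per arm: 1.965 × 173.1 × √(2/235) = 31.4

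The follow-up SD is not given. If it is s1, then b = (220.9² + s1² − 173.1²)/(2×220.9²), and the adjusted half-width is 31.4 × √[1 − (1 − b)²×220.9²/173.1²].

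| assumed s1 | b | adjusted half-width |
|---|---|---|
| 199 | 0.60 | 27.0 |
| 221 | 0.69 | 28.9 |
| 243 | 0.80 | 30.3 |
| 265 | 0.91 | 31.2 |
| 281 | 1.00 | 31.4 |

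**Stratum term.** If the stratum explains a share R² of the residual variance, the interval narrows by 1 − √(1 − R²): 0.5% at R² = 1%, 1.0% at 2% and 2.5% at 5%. These shares are assumed. The gain does not depend on b.

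**Validity.** I simulated 3,000 trials per setting: 470 subjects, 1:1 within strata, SD 200 at both times, and assumed stratum shares of 50/40/10%. The treatment-only ANOVA had bias within 0.3 cells/µL and coverage of 94.3% to 96.3%. With no stratum effect, mean CI width fell on adding baseline from 64.9 to 58.1 at slope 0.6, from 45.8 to 43.5 at slope 0.8 and from 22.9 to 22.6 at slope 0.95.

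An assumed stratum effect of 40 cells/µL per level adds variance 40² × 0.44 = 704.

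- At slope 0.8 the residual variance is 200² × 0.36 = 14,400, so R² = 704/15,104 = 4.7%. Adding the stratum to the baseline-adjusted model cut the width from 44.6 to 43.5. ANOVA coverage was 95.1%, so no conservatism was visible.
- At slope 0.95 the residual variance is 200² × 0.0975 = 3,900, so R² = 704/4,604 = 15%, well beyond the 0 to 5% range. The width fell from 24.6 to 22.7. ANOVA coverage was 96.3%, slightly conservative.

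**The case against.** The strongest case against is that this is a preference and not an error. The ANOVA is unbiased with a valid interval, nothing is decided on CD4+, and the gain may be close to zero. At r = 0.9 it is 2.5% or less for k from 1.0 to 1.2. That fairly limits the weight of the point but does not remove it: both covariates are already collected, and adjustment risks only about 0.1% of width.

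The protocol also does not say that treatment is the sole term; it is only the sole term listed. The Week 48 SAP may have added others, so the finding concerns the protocol text and not the model that was run.

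The Phase 2 SDs come from untreated patients starting therapy, with mean gains of 157 to 189 cells/µL by Week 24. They need not carry over to women already suppressed on long-term treatment, so those figures only show scale. Nothing in the documents shows that prior regimen predicts CD4+ change.

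Some stronger readings are tempting and are not supported:

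- A reader might count a chance baseline imbalance as a second harm, because it shifts the estimate by −(1 − b) times the imbalance. That shift is the source of the excess variance s0²(1 − b)², and the unadjusted interval already allows for it.
- A reader might cite SAP 3.3 (no stratification), 6.2.1 (descriptive CD4+ summaries) or 6.3 (no change from the protocol) as confirming the Week 48 model. Those sections belong to the final all-B/F/TAF analysis and neither govern nor corroborate the randomised comparison.
- A reader might conclude that nothing is lost when the slope is near 1. That holds for the baseline term only.

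**Conclusion.** The point holds as a minor efficiency improvement. As written, the protocol's CD4+ comparison is valid but leaves out two available terms. With equal SDs, baseline adjustment would narrow the interval by about 13%, 8% or 2.5% at assumed correlations of 0.5, 0.7 or 0.9. The gain is zero at a slope of exactly 1, and the worst case is a cost of about 0.1%. The stratum would add 0 to about 2.5% under an assumed 0 to 5% of residual variance; leaving it out makes the interval at most slightly conservative.

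The protocol wording and the algebra are certain. The size of the gain in this population is unknown, and so is the model used at Week 48. Someone might infer that the reported CD4+ result is biased or that the trial's conclusions are at risk; neither follows, and the primary endpoint is untouched.

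**What to change.** Specify in protocol 8.5.2 and the synopsis an ANCOVA of CD4+ change at Week 48 on treatment, continuous baseline CD4+ and prior-regimen stratum (three levels). Use the same model for the LOCF version, and still tabulate the unadjusted means.

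SAP 2.2 reports the Week 48 analysis as already conducted. If the ANOVA was used there, keep it as the reported comparison and present the ANCOVA in the study report as a labelled post hoc sensitivity analysis. If the Week 48 SAP already included these terms, only the protocol wording differs and no further analysis is needed.

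Before the Week 48 analysis this was a change of wording. It now costs one extra model for each of the two CD4+ versions, on existing data, and a note in the report.

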### 6.4. Treatment Assessments (Weeks 4-48)

The following evaluations are to be completed at the end of Weeks 4, 8, 12, 24, 36, and 48 unless otherwise specified.

Study visits are to be completed within  $\pm$  2 days of the protocol-specified visit date based on the Day 1 visit through Week 12 and completed within  $\pm$  6 days at Week 24 and Week 36, unless otherwise specified. The visit window at Week 48 will be  $\pm$  6 weeks of the protocol-specified visit date, and these clinical visit windows coincide with the Week 48 statistical analysis window for HIV-1 RNA.

Regularly scheduled evaluations will be made on all subjects whether or not they continue to receive study drug.

- Review of AEs and changes in concomitant medications
- Complete physical examination (**Weeks 24 and 48**) (urogenital/anorectal exams will be performed at the discretion of the Investigator) or symptom-directed physical examination as needed
- Vital signs measurement (blood pressure, pulse, respiration rate, and temperature), including weight
- 12-lead ECG performed supine (**Weeks 24 and 48**)
- Urine collection for the following laboratory procedures:
  - Urinalysis
  - Urine albumin, urine creatinine, urine protein, retinol binding protein and beta-2 microglobulin (**Weeks 24 and 48**)
  - Urine pregnancy test (females of childbearing potential only); positive urine pregnancy tests will be confirmed with a serum test. If the test is positive, subjects on GS-9883/F/TAF will be discontinued.
  - Urine storage sample for possible additional clinical testing

- Blood sample collection for the following laboratory analyses:
  - Chemistry profile: alkaline phosphatase, AST, ALT, GGT, total bilirubin, direct and indirect bilirubin, total protein, albumin, bicarbonate, BUN, calcium, chloride, creatinine, glucose, phosphorus, magnesium, potassium, sodium, uric acid, and amylase (reflex lipase testing is performed in subjects with total amylase  $> 1.5 \times$  ULN). At Weeks 12, 24 and 48, analyses of glucose will be done as part of the fasting metabolic assessments and not as part of the chemistry profile. At Weeks 24 and 48, TSH will also be analyzed.

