## **6.6. Post-Treatment Assessments**

### **6.6.1. Early Study Drugs Discontinuation (ESDD) Assessments**

If the subject discontinues study drug prior to the Week 48 Visit, the subject will be asked to return to the clinic within 72 hours of stopping study drug for the Early Study Drugs Discontinuation Visit. The subject will be asked to continue attending the scheduled study visits through the Week 48 Visit.

**At the Early Study Drugs Discontinuation Visit, any evaluations showing abnormal results indicating that there is a possible or probable causal relationship with the study drug, will be repeated weekly (or as often as deemed prudent by the Investigator) until the abnormality is resolved, returns to baseline, or is otherwise explained.**

The following evaluations are to be completed at the Early Study Drugs Discontinuation Visit:

- Review of AEs and changes in concomitant medications
- Complete physical examination (urogenital/anorectal exams will be performed at the discretion of the Investigator)
- 12-lead ECG performed supine
- Vital signs measurement (blood pressure, pulse, respiration rate, and temperature), including weight
- Urine collection for the following laboratory procedures:
  - Urinalysis
  - Urine pregnancy test (women of childbearing potential only); positive urine pregnancy tests will be confirmed with a serum test.
  - Urine storage sample for possible additional clinical testing
- Blood sample collection for the following laboratory analyses:
  - Chemistry profile: alkaline phosphatase, AST, ALT, GGT, total bilirubin, direct and indirect bilirubin, total protein, albumin, bicarbonate, BUN, calcium, chloride, creatinine, glucose, phosphorus, magnesium, potassium, sodium, uric acid, and amylase (reflex lipase testing is performed in subjects with total amylase  $> 1.5 \times$  ULN), and TSH
  - Estimated glomerular filtration rate according to the Cockcroft-Gault formula
  - Hematology profile: complete blood count (CBC) with differential and platelet count
  - Plasma HIV-1 RNA
  - CD4+ cell count
  - Plasma storage samples for safety, virology, or PK testing
  - Plasma HBV DNA (for subjects who meet the definition of HBV infection)
  - HIV-1 genotype/phenotype testing for subjects with virologic failure
- Drug accountability

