#### **8.1.3. Secondary Endpoint**

Secondary endpoints include:

- The proportion of subjects with HIV-1 RNA  $<$  50 copies/mL at Week 48 as determined by the US FDA-defined snapshot algorithm
- The change from baseline in CD4+ cell count at Week 48

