### 8.3. Data Handling Conventions

HIV-1 RNA results of 'No HIV-1 RNA detected' and "< 20 cp/mL HIV-1 RNA Detected" will be imputed as 19 copies/mL for analysis purpose. Laboratory data that are continuous in nature but are less than the lower limit of quantitation or above the upper limit of quantitation will be imputed to the value of the lower or upper limit plus or minus one significant digit, respectively (e.g., if the result of a continuous laboratory test is < 20, a value of 19 will be assigned).

Missing data can have an impact upon the interpretation of the trial data. In general, values for missing data will not be imputed. However, a missing pre-treatment laboratory result would be treated as normal (ie, no toxicity grade) for the laboratory abnormality summary.

All available data for subjects that do not complete the study will be included in data listings.

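### The only supplement to the observed-data CD4+ analysis is LOCF, which does not estimate the Week 48 change; a repeated-measures model on the scheduled visits would

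*Protocol*

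**What the plan says.** Protocol section 8.1.3 lists as a secondary endpoint "The change from baseline in CD4+ cell count at Week 48". Under section 8.5.2 the between-group differences and 95% CIs "will be constructed using ANOVA models, including treatment (GS-9883/F/TAF vs. SBR) as a fixed effect in the model"; no visit term or other effect is named. Section 8.3 sets the default: "In general, values for missing data will not be imputed". The ANOVA therefore uses women with a Week 48 value. Section 8.5.2 then closes with the supplement, introduced as an addition to the ANOVA: "missing CD4+ cell count will be imputed using Last Observation Carried Forward (LOCF) method and analyzed similarly".

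The synopsis says of the laboratory analyses, HIV-1 RNA, CD4+ count and physical examinations that they "will be performed at the Screening, Day 1, and all subsequent study visits". Section 6.4 fixes the post-baseline schedule: "The following evaluations are to be completed at the end of Weeks 4, 8, 12, 24, 36, and 48". Of a woman who stops study drug before Week 48, section 6.6.1 says: "The subject will be asked to continue attending the scheduled study visits through the Week 48 Visit".

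The supplied SAP covers only the final all-B/F/TAF analysis (sections 2.3 and 3). Its section 6.2.1 summarises CD4+ from observed on-treatment data with missing values excluded, and uses no LOCF. Section 2.2 reports that the Week 48 analysis has been conducted. The detailed plan for that analysis is not among the documents, and neither supplied document describes a repeated-measures model.

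**The concern.** A supplementary missing-data analysis should address the same quantity as the main analysis under a different assumption about the missing values. LOCF changes the quantity. It reports a mixture of Week 48 changes and changes at the last visit attended. If it agrees with the ANOVA, that says little about robustness. If it disagrees, the gap may come from the carried values alone. Meanwhile the ANOVA uses none of the CD4+ counts from Weeks 4 to 36, although they are collected.

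At stake is how well the CD4+ difference is supported. Some reasons for stopping are arm-specific by design: a confirmed pregnancy ends GS-9883/F/TAF but not necessarily the comparator (section 6.4, Appendix 6), and the hyperbilirubinemia rules in section 7.5.6 are written around atazanavir. Unequal dropout is therefore possible. The documents do not say how large it would be.

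**Working it through.** **The plan's own figures.** The documents give no SD, dropout rate, power or interval width for CD4+ in this trial. The one power figure concerns the primary endpoint: Φ(0.04/√(2×0.02×0.98/235) − 1.96) = 87.2%, matching the stated 87% or more. CD4+ does not enter it.

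**Inputs.**
- 235 women per group (section 8.8).
- CD4+ visits at Weeks 4, 8, 12, 24, 36 and 48 (section 6.4).
- Assumed: dropout d₁ (switch) and d₀ (SBR) of 5% to 15%; a linear CD4+ change of t₁ and t₀ cells/µL by Week 48; last visit equally likely to be Week 4, 8, 12, 24 or 36; dropout unrelated to CD4+.

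**Bias by formula.** The mean last week is (4+8+12+24+36)/5 = 16.8. A carried value therefore misses, on average, the fraction (48 − 16.8)/48 = 0.65 of the change. The bias in the LOCF difference is −0.65 × (d₁t₁ − d₀t₀).

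| Dropout, switch / SBR | Change by Week 48, switch / SBR | LOCF bias by formula |
|---|---|---|
| 10% / 10% | +20 / +20 | 0 |
| 10% / 5% | +20 / +20 | −0.65×(2−1) = −0.65 |
| 15% / 5% | +40 / +40 | −0.65×(6−2) = −2.6 |
| 15% / 5% | +50 / +50 | −0.65×(7.5−2.5) = −3.25 |
| 10% / 10% | +40 / +20 | −0.65×(4−2) = −1.3 |
| 10% / 10% | +40 / 0 | −0.65×(4−0) = −2.6 |

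**Bias by simulation.** There were 600 replicates per scenario, with a random intercept (SD 170) and serially correlated residuals (SD 110).
- 15% / 5% dropout, +50 in both groups: LOCF −3.3, observed-case ANOVA +0.2, repeated-measures estimate +0.1.
- 10% / 10% dropout, +40 against +20: LOCF −1.7, observed-case −0.4, repeated-measures −0.5.
- 10% / 10% dropout, +20 in both groups: LOCF +0.3, observed-case +0.5, repeated-measures +0.5.

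The Monte Carlo standard error of each mean is about (28/1.96)/√600 = 0.6, so these agree with the formula. Where dropout is unrelated to CD4+, the observed-case ANOVA has no bias and LOCF introduces one.

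**Width.** At 10% missing in both groups the 95% half-widths were 28.3 (observed-case), 26.2 (LOCF) and 28.1 (repeated measures). LOCF's reported 26.2 is close to its empirical 1.96 × SD of 26.5. A separate simulation at 10% missing gave a reported standard error of 14.45 against a true sampling error of 14.50, with 94.9% coverage.

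**The case against.** The case for leaving the plan alone is substantial.

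- **LOCF is only a supplement.** The sentence begins with the words for an addition, and section 8.3 makes observed data the default. A reader might infer that LOCF is how missing Week 48 counts are mainly handled; the text does not support that.
- **Carried values need not be early.** They can come from Week 36. Women who stop drug are asked to keep attending, CD4+ is drawn at the early discontinuation visit, and the Week 48 visit window is ±6 weeks. Only early and complete losses are frozen at an early value. This stands, with one limit: section 8.5.2 does not say whether CD4+ values taken after stopping drug are used.
- **The assumptions may be generous.** The nearest dropout figure in the documents is 2 of 98 (2.0%) by Week 24 in the Phase 2 study, in a different population. These women are suppressed and have completed Week 48 OLE, Week 96 or Week 144 of earlier studies, so a steep CD4+ trend is not evident. With 2% dropout in one arm only and a +50 trend, the bias is 0.65 × 0.02 × 50 = 0.65 cells/µL.
- **The replacement gains little precision** over the ANOVA already planned (28.1 against 28.3), and it too is biased if dropout depends on unobserved CD4+.
- **No decision rests on this interval.**

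All of this limits the size of the point. None of it makes LOCF an estimate of the Week 48 change.

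**Conclusion.** The point holds as a minor one. The sole supplement to the observed-data ANOVA targets the wrong quantity. Under the assumptions above it is off by about 2 to 3 cells/µL when the trend or effect is +40 to +50, by about 1 when the arms differ by 20, and by nearly nothing when dropout and trends are equal. Dropout, trend and SD are all assumed, because the documents supply none of them for this endpoint.

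A reader might also infer that the LOCF standard error is too small by the factor √(1 − m), that is 0.975, 0.949 or 0.922 for m = 5%, 10% or 15% missing. The check does not support this. LOCF intervals are narrower than observed-case ones, but they match LOCF's own sampling variation. Each carried value is a real measurement from another time. The fault is in what is estimated, not in the stated precision.

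Nor does the point touch the primary analysis, the sample size or any conclusion of non-inferiority. The absence of LOCF from the supplied SAP is not a contradiction either, since that SAP does not contain the Week 48 comparison.

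**What to change.** Keep the observed-data ANOVA. Replace the supplementary LOCF analysis with a mixed model for repeated measures on CD4+ change from baseline at Weeks 4, 8, 12, 24, 36 and 48. Use fixed effects for treatment, visit and treatment-by-visit and an unstructured within-subject covariance, and report the Week 48 difference with its 95% CI.

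The cost is small: a sentence of plan text, standard code and no new data. The interval will be somewhat wider than under LOCF (28.1 against 26.2 in the 10% scenario, about 7%), and the model relies on data being missing at random, which should be stated. Because the Week 48 analysis has already been run, the result should be labelled as a re-analysis and documented as such in the study report. If the Week 48 plan, which was not available here, already contains such a model, it is enough to point to it.
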